8.8 MMRM Analyses

Figure 17 will be a line graph of least squares predicted mean values over time based on the mixed model for repeated measures (MMRM). This figure will summarize the MMRM results for values over time.

Figure 18 will be a line graph of least squares predicted mean change values over time based on the mixed model for repeated measures (MMRM). This figure will summarize the MMRM results for values over time.

8.9 Critical care and hospital stay parameters, to be measured until Day 28

The following critical care and hospital stay parameters will be assessed in the mITT analysis set.

- o ICU free days
- o Days in ICU
- Days on ventilator
- Ventilator free days
- Vasopressors days
- o Vasopressors free days
- Hospital length of stay (days)

Because of the expected skewness in the distributions of these parameters, non-parametric Wilcoxon rank sum tests will be used assess the statistical significance of treatment group differences in these parameters. Table 14.2.4.1 will provide summary statistics by treatment groups including mean, median, standard deviation, 25th percentile, 75th percentile, minimum, and maximum values. Analyses will focus on clinical effect sizes. The non-parametric clinical effect size to be used is the concordance statistic (c-stat) determined from a logistic regression. The c-stat is the probability that a randomly selected subject treated with Reltecimod has a better outcome (e.g., more free-days) than a randomly selected placebo subject and is related to the area under a receiver operating characteristic (ROC) curve²⁵. Graphical comparisons of distributions between treatment groups will be provided using box and whiskers plots (Figures 19 to 25).

Table 14.2.4.2 will summarize hospital discharge status in the mITT analysis set.

Table 14.2.4.3 will summarize hospital readmissions in the mITT analysis set.

Table 14.2.4.4 will summarize critical care and hospital stay parameters over days 1 to 28 comparing NICCE successes to NICCE failures. Figures 26 to 33 will graphically compare these distributions using box and whiskers plots.

²⁵ Hanley JA and McNeil BJ. The Meaning and Use of the Area under a Receiver Operating Characteristic Curve (ROC), Radiology 1982: 143: 29-36.

Additional graphical analyses will include displaying the percentages of patients staying in the ICU, needing ventilation, and staying in the hospital over time by treatment group (Figures 34, 35, and 36).

Table 14.2.4.5 will summarize critical care and hospital stay parameters over days 1 to 28 comparing subjects with and without freedom from durable loss of renal function status among patients in the mITT analysis presenting with Stage 2 or Stage 3 AKI.

Tables 14.2.4.6, 14.2.4.7, and 14.2.4.8 repeat the treatment group comparisons of critical care and hospital stay parameters, hospital discharge status, and hospital readmissions, but in the Per Protocol analysis set.

8.10 Clinical local parameters (debridements)

The following debridement secondary endpoints were specified:

- o Number of debridement to days 7, 10, 14
- o Proportion of patients needing (up to Day 14):
 - only one debridement to control the infection
 - 2 debridements to control the infection
 - 3 debridements to control infection
 - >3 debridements to control the infection
 - >3 debridements to control infection

Tables 14.2.5.1 will summarize the cumulative numbers of debridements to Days 7, 10, and 14, using means, medians, standard deviations, and ranges. Wilcoxon rank-sum tests will be provided for descriptive pair-wise group comparisons.

Table 14.2.5.2 will summarize the proportions of patients requiring only one debridement, 2 debridements, 3 debridements, \geq 3 debridements and > 3 debridements up to an including Day 14 for all patients in the mITT Analysis Set and for both treatment groups. Chi-square tests will be used to assess the degree to which observed treatment difference could be attributable to chance variation.

Figure 37 will graphically display the data from Table 14.2.5.1. Figure 38 will graphically display the data from table 14.2.5.2.

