These bacteria produce a variety of exotoxins, including among others, toxins known as superantigens which bypass the normal immune response for processing bacterial antigens, are a major inducer of the inflammatory response, and can spread into the systemic circulation. This leads to massive polyclonal expansion with the release of pro-inflammatory cytokines, causing a T helper 1 "cytokine storm" and subsequent refractory shock and multi-organ failure.

NSTI is a rare disease, with an estimated prevalence of 4.5 cases per 100,000 individuals in Europe and 6.8 cases per 100,000 in the US. Risk factors appear to be diabetes, obesity, intravenous drug use, peripheral vascular disease and immunosuppression. However, a large proportion of NSTI patients have no predisposition for their infection $^{3-5,8}$.

NSTI is different from milder superficial skin infections with regard to clinical presentation, treatment strategies, coexisting systemic manifestations and its fatal outcome⁷. Although the survival of patients with NSTI has improved throughout recent

years^{17–21}, mortality rates are still unacceptable, with up to 17% according to reports from 2006 to $2011^{1,2,8,22}$.

Patients with NSTI require emergent operative and repeated exploration with wide debridement of all necrotic tissue, with acute resuscitation along with administration of broad spectrum antibiotics with specific coverage for methicillin-resistant *Staphylococcus aureus* (MRSA), beta haemolytic Streptococcus and clostridia, and patients with extensive necrosis of an extremity may require amputation. The duration of intensive care unit (ICU) stay is usually dependent on the degree of organ dysfunction and the need for mechanical ventilation for respiratory failure. The duration of hospital stay is dependent on the duration of antibiotic therapy and wound management issues.

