4.2 Primary Endpoint Components and Other mSOFA Related Outcomes

The primary endpoint components and other mSOFA related outcomes will be evaluated as additional secondary efficacy endpoints in descriptive treatment group comparisons using the statistical methods summarized below.

- Distribution of mSOFA scores at Day 14
- Kaplan-Meier analysis of the time to resolution of mSOFA score to ≤ 1 with censoring at Day 14
- Kaplan-Meier analysis of the time to resolution of mSOFA score to ≤ 1 up to Day 28
- Single components of the primary composite end point:
 - o Alive at Day 28
 - o Debridements by Day $14 \le 3$
 - Number of amputations (removal of a limb or portion of a limb to the level of a joint space) (done after first debridement)
 - o mSOFA score on Day $14 \le 1$
 - o Reduction of ≥3 score points between baseline and Day 14 mSOFA score.
- Clinical local parameters:
 - Number of debridements to days 7, 10, and 14 Proportion of patients needing (up to Day 14):
 - only one debridement to control the infection
 - 2 debridements to control the infection
 - 3 debridements to control the infection
 - \geq 3 debridements to control the infection
 - >3 debridements to control the infection

- Clinical systemic parameters:
 - Evaluation of organ function over time, using mSOFA score (total score and organ specific score)

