4.3 Critical care and hospital stay parameters

The following critical care and hospital stay parameters will be measured up to Day 28. These parameters relate to medical and procedures costs:

- o ICU free days
- o Days in ICU
- o Days on ventilator
- Ventilator free days
- Vasopressors days/ Vasopressors free days
- Hospital length of stay (days)

Outcomes like duration of mechanical ventilation and incidence of organ failure may be lower in the group with higher mortality simply because of the competing effect of mortality (Rubenfeld, Angus et al. 1999⁷). Patients who die are not at risk to develop further organ failures or prolonged ventilator dependence. One proposed solution to this problem is to calculate life-support-free days. For example, ventilator-free days can be calculated over a predefined measurement period of (typically) 28 days. Patients who die or are mechanically ventilated longer than this period are assigned zero ventilator-free days for any days on which the patient is not alive or any day beyond the 28 days. All survivors accrue one ventilator-free day for each day after entry into the study that they are both alive and free of mechanical ventilation. By combining mortality and morbidity in one measure, the free-day outcome avoids the problem of competing mortality. A similar approach will be used to determine ICU-free days and vasopressors free days.

The 28-day horizon will be used when determining ICU-free days, vasopressor-free days, and mechanical ventilation-free days. ICU time will be calculated using calendar days starting on the day of admission to the ICU and ending on the day of ICU discharge inclusive.

A vasopressor-free day or ventilator-free day will be defined based on a calendar days starting from the day of drug administration. Any day upon which a patient experienced no part of a calendar day on a vasopressor or a ventilator is a ventilator/vasopressor free day. For example, if the patient was on a ventilator for one hour on any given day, or for even one minute, this day will not count as a ventilator-free day. The same method will be used in calculating vasopressor-free days; a vasopressor-free day means a day alive and not on a vasopressor at any time during that day. This method is a convention generally accepted for these parameters. Events that occur under general anesthesia are not counted. Hospital length of stay will be calculated according the total number of calendar days in the hospital.

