8.1 Primary and Conditional Co-Primary Endpoint in mITT Analysis Set

The numbers and percentages of patients in the mITT analysis for each group meeting the primary efficacy endpoint (NICCE) and the conditional co-primary efficacy endpoint (CCPE) are summarized in Tables 14.2.1.1 and 14.2.1.2, respectively. These tables include the statistical significance of the group difference based on unadjusted two-sided chi-square statistics. Study success requires $p \le 0.01$ for the primary endpoint and $p \le 0.05$ for the conditional co-primary endpoint. These tables also provide the estimated treatment group differences for both endpoints as well as the 99% confidence interval for the primary endpoint and the 95% confidence interval for the conditional co-primary endpoint. Figures 1 and 2 will be bar charts that illustrate these primary study results. Figures 3 and 4 will be forest plots that summarize the point estimates and confidence intervals of the endpoints and their components.

Tables 14.2.1.1 and 14.2.1.2 also summarize the components of the NICCE and the conditional co-primary endpoint. P-values are provided for descriptive purposes only since there were no *a priori* hypotheses concerning the components, other than they would generally show group differences in the same direction. 95% confidence intervals are provided in order to facilitate an evaluation of the statistical precision in the estimated group differences.

The components of NICCE are:

- Alive at Day 28
- <=3 debridements through Day 14
- No amputation beyond first debridement
- mSOFA score of <=1 at Day 14
- Reduction of >= 3 between baseline and Day 14 in mSOFA

The components of the conditional co-primary endpoint (CCPE) are:

- Alive at Day 28
- <=3 debridements through Day 14
- No amputation beyond first debridement

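### SAP 8.10 gives no rule for deaths before Day 14 in the debridement tables, so an early death after one operation is tabulated as infection controlled with a single debridement

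*SAP*

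**What the plan says.** SAP 8.10 specifies two debridement tables. Table 14.2.5.1 summarises cumulative counts to Days 7, 10 and 14, and "Wilcoxon rank-sum tests will be provided for descriptive pair-wise group comparisons". Table 14.2.5.2 gives the proportions with 1, 2, 3, ≥3 and >3 debridements "up to an including Day 14 for all patients in the mITT Analysis Set and for both treatment groups", with chi-square tests. SAP 4.2 labels the best category "only one debridement to control the infection". SAP 4.6 repeats both tables across subgroup classifications 1 to 11.

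SAP 8.1 adds that Tables 14.2.1.1 and 14.2.1.2 "also summarize the components of the NICCE and the conditional co-primary endpoint", so the debridement and amputation components also appear as single rows.

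None of SAP 4.2, 8.1 and 8.10 or Protocol 7.2 and 9.2.4 says how a patient who dies before Day 14 is placed in these tables. The failure rule in SAP 5.10.2 covers only the two composites.

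Elsewhere the SAP does deal with death. SAP 4.3 warns that some outcomes "may be lower in the group with higher mortality simply because of the competing effect of mortality" and adds free-day measures for ICU, ventilator and vasopressor use. SAP 5.2 bars carrying mSOFA forward after death. SAP 8.7 treats deaths before Day 14 as never having resolved.

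**The concern.** Death ends further debridement. A literal count in all mITT patients puts someone who died on Day 2 after one operation in the category that claims the infection was controlled by that operation. The same patient ties with the best survivors in the Wilcoxon test. The label is false for that patient, and the comparison mixes surgical need with survival time.

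Deaths are not rare in this disease: Protocol 1.1.1 states that "mortality rates are still unacceptable, with up to 17% according to reports from 2006" to 2011. Fewer debridements is also how Protocol 2.4 proposes to measure local benefit, and the individual components are a secondary objective in Protocol 2.2. SAP 8.1 states no prior hypotheses for the components "other than they would generally show group differences in the same direction". A drug that keeps severely ill patients alive long enough to need further surgery could look worse on the one-debridement row, and a drug with more early deaths could look better.

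**Working it through.** **Plan's own figures.** The documents give no figure for the debridement endpoints. Their power figures reproduce at 145 per arm: NICCE 99.6%, 95.9% and 80.2% (stated 99%, 95.9%, 80.2%); CCPE 96.4% and 84.8% (as stated).

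**Inputs from the documents.** 145 per arm (SAP 2.4.1). Phase 2 placebo: 20% with one debridement and 30% with four or more, so 70% with three or fewer. Phase 2 mortality: 20% placebo, 6.7% at 0.5 mg/kg (Protocol Table 3).

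**Assumptions.** The share m dying before Day 14 in each arm; the share f of those deaths that falls in the favourable category; and the survivors' rate q, set to the Phase 2 placebo rate and equal in both arms, so that there is no true local effect.

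**Formula.** The observed favourable rate in an arm is m·f + (1 − m)·q. Subtracting the arms gives

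artefact = (m_high − m_low) × (f − q).

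It favours the arm with more early deaths only when f > q.

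**One debridement, q = 0.20, early deaths 15% vs 5%.**
- f = 0.6: 26% vs 22%; 0.10 × 0.4 = +4.0 points; chance of nominal p < 0.05 favouring the arm with more deaths 12%, against 2.5% expected.
- f = 1: 32% vs 24%; 0.10 × 0.8 = +8.0 points; chance 33%.
- Standard error at f = 1: √[(0.32×0.68 + 0.24×0.76)/145] = 5.3 points; at f = 0.6 it is 5.0.

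The Phase 2 mortality gap (13.3 points), with every death placed before Day 14 and f = 1, gives 0.133 × 0.8 = +10.6 points. That is an upper range.

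**Three or fewer, q = 0.70, early deaths 15% vs 5%.** f = 1, 0.8 and 0.6 give +3.0, +1.0 and −1.0 points. The sign depends on how many of those who die early had already passed three debridements.

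**No later amputation, 15% vs 5%, assumed q = 0.85 to 0.90, f = 1.** +1.5 to +1.0 points. Here the relevant deaths run to Day 28.

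**Wilcoxon test.** This was simulated with the same debridement process in both arms (1 + Poisson(1.7), extra procedures spread over Days 1 to 8), Phase 2 mortality, and an assumed 30% to 60% of deaths in the first four days. The c-statistic for the drug is 0.485 to 0.472 when deaths are counted as observed. It is about 0.54 to 0.55 when deaths rank worst. The null is 0.5 and the standard error 0.033.

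**The case against.** The case for leaving the plan alone has four parts.

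**A death-adjusted local endpoint already exists.** CCPE requires survival to Day 28, at most three debridements and no later amputation. It is formally tested and needed for study success (SAP 2.1.3, 2.2). Survival is also shown in the same component tables. This stands, and is why the component definitions need no change.

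**Everything affected is descriptive.** SAP 8.1 says "P-values are provided for descriptive purposes only since there were no" prior hypotheses about the components, and SAP 5.6 and 5.7 make no multiplicity adjustment for these endpoints. This stands and limits the consequence. It does not make the category label true.

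**Ranking deaths worst replaces one distortion with a larger one.** In the simulation, counting as observed is 0.5 to 0.8 standard errors from the null, and worst ranks are 1.2 to 1.5 away in the other direction. The second analysis reads a mortality difference as a local one. This stands against making it the main test.

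**Early deaths are partly limited.** Exclusions 6, 10 and 11 in Protocol 3.2 remove some patients likely to die soon, and the optional PP set drops deaths within one day of dosing (SAP 2.6). This helps little, because Tables 14.2.5.1 and 14.2.5.2 are mITT only.

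A reader might infer that these tables always favour the more lethal arm, or that the row for three or fewer debridements is off by 6.7 to 12.0 points (0.133 × f, f = 0.5 to 0.9). The documents do not support this. No SAP sentence scores death as a good outcome, and f and the timing of deaths are not given. The product 0.133 × f is the gap between two scoring rules. The artefact is 0.133 × (f − 0.70), which runs from −2.7 to +2.7 points over the same range.

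**Conclusion.** The gap is real and limited. SAP 8.10 as written misclassifies early deaths in Table 14.2.5.2 and gives them favourable ranks in Table 14.2.5.1 and in the subgroup repeats of both tables.

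The one-debridement category is the row that matters. An artefact of 4 to 8 points, against a standard error of about 5, is plausible if early deaths differ by 10 points and most of them follow a single operation. The rows for three or fewer debridements and for amputation are affected only slightly, and the former has no fixed direction.

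Which arm gains cannot be known in advance. On the Phase 2 mortality pattern the artefact would work against the drug. All sizes rest on assumed early-death shares and f, and on Phase 2 placebo rates standing in for survivors' rates.

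**What to change.** In Table 14.2.5.2, add a category for death by Day 14 and define the 1, 2, 3, ≥3 and >3 categories as alive at Day 14 with that count. Keep all mITT patients in the denominator. In the 15% vs 5% example, the one-debridement row becomes 0.85 × 20% = 17.0% vs 0.95 × 20% = 19.0%, with the deaths visible beside it.

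In Table 14.2.5.1, keep the raw counts and show deaths by Days 7, 10 and 14 beside them. Add a Wilcoxon test with deaths ranked worst as a sensitivity analysis, labelled as combining mortality with debridement.

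Leave the NICCE and CCPE components as defined. Footnote in Tables 14.2.1.1 and 14.2.1.2 how many deaths are counted as meeting each local component. Carry the same changes into the subgroup repeats and Figures 37 and 38.

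The cost is SAP wording and minor table programming before unblinding, with no new data. The downside is that the alive-with-count categories carry some mortality information (the −2.0 points above arise with no local effect), so the raw counts should stay as a descriptive line.

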8.11 Freedom from Durable Loss of Renal Function

Tables 14.2.6.1.1 to 14.2.6.6 summarize AKI at pre-dose screening and Maximal AKI determined over the first seven days though independent adjudication.

Tables 14.2.6.2.1 to 14.2.6.2.4 summarize treatment group comparisons of the AKI endpoints at Day 28 including the key secondary endpoint, *Achieving Freedom from Durable Loss of Renal Function at Day 28* and the exploratory endpoint, *Improvement in Durable Loss of Renal Function at Day 28*. The summarized analyses differ with regard to whether there was algorithmic determination (primary) or independent adjudication of reference creatinine (sensitivity analysis) and whether the algorithmic determination of Day 28 status was based on LOCF (primary) or using the mean value over days 14 to 28 (sensitivity analysis). The results from Table 14.2.6.2.1 will contain the results from the key secondary endpoint.

Tables 14.2.6.3.1 to 14.2.6.3.3 summarize treatment group comparisons of the AKI endpoints at Day 14 including *Achieving Freedom from Durable Loss of Renal Function at Day 14* and *Improvement in Durable Loss of Renal Function at Day 14*. The summarized analyses differ with regard to whether there was algorithmic determination or independent adjudication of reference creatinine and whether there was algorithmic or independent adjudication of Day 14 status.

Figure 39 will graphically summarize the percentages of subjects in each group achieving *Freedom from Durable Loss of Renal Function* at Days 14 and 28. Similarly, Figure 40 will graphically summarize the percentages of subjects in each group achieving *Improvement in Durable Loss of Renal Function* at Days 14 and 28.

Tables 14.2.6.4.1 to 14.2.6.4.2 summarize treatment group comparisons of AKD stage at Day 28. The summarized analyses differ with regard to whether there was algorithmic determination or independent adjudication of reference creatinine.

Tables 14.2.6.5.1 to 14.2.6.5.3 summarize treatment group comparisons of AKD stage at Day 14. The summarized analyses differ with regard to whether there was algorithmic determination or independent adjudication of reference creatinine and whether Day 14 status was determined algorithmically or through independent adjudication.

8.12 C - reactive protein (CRP)

Table 14.3.4.1 summarizes CRP at Screening, at Day 14, and changes from Screening to Day 14 for CRP values by treatment group in the mITT Analysis Set.

9 Presentation of Safety Evaluations

9.1 Adverse Events

Treatment-emergent AEs (TEAE) reported during the study will be summarized by treatment group according to Medical Dictionary for Regulatory Activities (MedDRA) System Organ Class (SOC) and Preferred Term (PT). Incidence rates of TEAE will be tabulated by class. The distributions of severity will be provided for drug-related AEs, separately by treatment group. Further tabulations by relationship and severity of AE may be provided.

9.1.1 Summary of adverse events

All analyses of adverse events will be based on the As Treated (Safety) Analysis Set. A summary of the numbers and percentages of patients within each treatment group experiencing at least one treatment emergent adverse event (TEAE) will be provided in Table 14.3.1.1. TEAEs will be defined as an AE occurring from Day 1 to end of study which is defined as Day 28. 'Drugrelated' is defined as 'possibly', 'probably', or 'definitely' caused by the study medication.

The AE endpoints summarized in this table are:

- With one or more TEAE
- With one or more drug-related TEAE
- With one or more serious TEAEs
- With one or more serious drug-related TEAE
- With one or more severe TEAE
- With one or more moderate or severe TEAE
- TEAE with outcome of death
- TEAE with outcome of drug related death
- Discontinued study drug due to AE/SAE
- Discontinued from study due to AE/SAE

9.1.2 Specific adverse events

The incidence rates (%) and event counts of TEAEs by system organ class (SOC) and by preferred term (PT) will be summarized by treatment group in Table 14.3.1.2. This table will be organized so that adverse event categories (SOC) are reported in upper case letters and specific adverse events (PT) are reported in lowercase.

Table 14.3.1.3 will summarize the incidence rates (%) of specific TEAE PTs, sorted by descending incidence of PT in the active drug group.

The incidence rates (%) and event counts of drug-related TEAEs by SOC and by PT will be summarized by treatment group in Table 14.3.1.4.

The incidence rates (%) and event counts of serious drug-related TEAEs by SOC and by PT will be summarized by treatment group in Table 14.3.1.5.

Table 14.3.1.6 will summarize the incidence rates (%) of serious TEAE PTs, sorted by descending incidence of PT in the active drug group.

The incidence rates (%) and event counts of serious drug-related TEAEs by SOC and by PT will be summarized by treatment group in Table 14.3.1.7.

